A Novel Telehealth Intervention using Nutrition and Exercise to Extend Intervention Benefits:
Enhancing Physical Function in the Long-term for Obese Older Adults

Pro 00105630

Version 1.0

4/24/2020

NCT04490356

Regulatory Sponsor: [name] [name]
Duke University
Department of Orthopaedic Surgery
[name]
[name]
[name]
[name]

Funding Sponsor: National Institutes of Health (NIH)

Study Summary

Title	A Novel Telehealth Intervention using Nutrition and Exercise to Extend Intervention Benefits: Enhancing Physical Function in the Long-term for Obese Older Adults
Short Title	Enhancing Physical Function in the Long-term for Obese Older Adults
Protocol Number	Pro00105630
Phase	N/A
Methodology	Qualitative individual interviews and/or focus groups will be conducted in-person or via the phone with: obese older adults who previously (within the last 20 months) participated in a weight loss intervention Single-arm pilot intervention investigating the feasibility, fidelity, and acceptability of a tele-nutrition and tele-exercise 3 month weight maintenance intervention
Study Duration	1 year
Study Center(s)	Single-center
Objectives	This study seeks to develop and test the feasibility, acceptability, and fidelity of a tele-nutrition and tele-physical activity weight-maintenance intervention tailored towards obese older adults who recently lost weight.
Number of Subjects	Up to 60 (Aim 1: up to 30; Aim 2: up to 20)
Diagnosis and Main Inclusion Criteria	Past participants of weight loss intervention for obese, older adults
Study Product, Dose, Route, Regimen	N/A
Duration of administration	N/A
Reference therapy	N/A
Statistical Methodology	We plan to use applied thematic analysis for the semi-structured interviews and focus groups. Descriptive statistics, proportions for feasibility, adherence and retention will be calculated, and student's t-test will be conducted to compare weight change over time in the pilot study.

1 Introduction

This document is a protocol for a human research study. This study is to be conducted according to US and international standards of Good Clinical Practice (FDA Title 21 part 312 and International Conference on Harmonization guidelines), applicable government regulations and Institutional research policies and procedures.

1.1 *Background*

[figure not shown]

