4.1 Inclusion and Exclusion Criteria

From Aim 1a and Aim 2: All potential participants will have previously participated in a weight loss intervention conducted by the [name] Nutrition Lab and checked the box on their consent form that states, "Yes, I agree to be contacted about potential future follow-up and future research studies."

Study staff will contact potential subjects to request their participation in the study. If potential subjects express interest, they will go through a phone screening process to determine initial eligibility. If potential subjects pass the screening process, they will be sent a consent form through REDcap and a virtual consent appointment will be scheduled.

Aim 1a:

We will contact our past participants, who previously agreed to be contacted for future research study, and successfully completed a lifestyle intervention (lost at least 3% body weight and increased short physical performance battery (SPPB) score by 1 point or 6-minute walk test (6MWT) by 50 meters) within the last 6 to 24 months. Inclusion/Exclusion criteria is below:

Table 1. Inclusion/Exclusion Criteria Aim 1a

Inclusion Criteria	Exclusion Criteria

Participated in a weight loss intervention in the last 6 to 18 months and lost \geq 3% body weight and improved SPPB score by \geq 1 point or 6MWT by \geq 50 meters (Perera et al. J Am Geriatr Soc. 2006;54(5):743-9)Age \geq 60Able to speak and understand spoken and written English.	
Presence of unstable or symptomatic life-threatening illnessNeurological conditions causing functional impairment, including Parkinson's disease, multiple sclerosis, and permanent disability due to strokeInability to complete physical function assessmentUnwilling to have their individual interview audio recordedHistory of cognitive impairment

Aim 2: Participants who agreed to be contacted for future research studies will be recruited from our on-going weight loss interventions and inclusion and exclusion criteria is below:

Table 3. Inclusion/Exclusion Criteria Aim 2

Inclusion Criteria	Exclusion Criteria
--------------------	--------------------

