SPPB (6, 64, 66)	0, 6, 12 weeks	Balance (side-by-side, semi-tandem, tandem), gait speed (4-meter timed walk), strength (chair stands).
6-minute walk test (aerobic endurance)	0, 6, 12 weeks	As many walking laps as possible in six minutes between cones placed 40 meters apart
Questionnaires		
Quality of Life; Mood; Depression; Stress; Sleep; Life Satisfaction	0, 6, 12 weeks	SF-36; CES-D; Perceived stress; Pittsburgh sleep
Acceptability		
Participant Satisfaction Questionnaire	12 weeks	Participants will be asked to rate their satisfaction using a five point Likert scale (very dissatisfied; dissatisfied; neutral; satisfied; very satisfied) on a) satisfaction with the delivery of the tele-nutrition intervention, b) satisfaction with the delivery of the tele-exercise intervention c) satisfaction with their ability to maintain their physical function d) satisfaction with their ability to maintain their weight loss e) satisfaction with interactions with the registered dietitian.
Feedback Session	12 weeks	Using an interview guide we will examine aspects of the program in-depth from participants' perspectives.
Attrition Rate	12 weeks	Attrition Rate (%) = (Number of dropouts ÷ number of total participants) x 100
Feasibility		
Feasibility	12 weeks	Proportion of participants recruited will be calculated as the number of patients deemed potentially eligible and contacted for enrollment divided by the total number of patients enrolled.
Fidelity		
Adherence to tele-nutrition intervention	12 weeks	Proportion adherent to the tele-nutrition intervention will be computed by dividing the number of participants who maintained their weight by the total number of participants
Adherence to the tele-exercise intervention	12 weeks	Proportion adherent to the tele-exercise intervention will be computed by dividing the number of participants who maintained their functional status by the total number of participants
Retention	12 weeks	Proportion retention will be computed by dividing the number of retained subjects at the end of the intervention by the total number of participants

Risk/Benefit Assessment

The risk to human subjects for participation in this study is minimal compared to the potential health benefits they will receive from participating in the interventions and receiving detailed nutrition and exercise information.

Physical Risks:

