Aim1a: A qualitative analytical approach is well suited to exploring concepts related to a complex process (long-term adherence to weight loss and physical activity). We plan to use applied thematic analysis, organizing the data in response to the a priori questions contained in the semi-structured interviews and interview guides. Interview guide questions will be developed utilizing input from the Interventionist and socio-behavioral researchers. We will use applied thematic analysis to analyze the data. Audio recordings will be transcribed verbatim following a transcription protocol. Two analysts will use NVivo 12 software to develop and apply structural (a priori) codes to segment participants' narratives into conceptual categories (e.g., all text describing a similar concept, such as psychosocial factors). Next, analysts will identify and apply content-driven (emergent) codes to the text for each of the conceptual categories (e.g., potential themes related to psychosocial factors). Inter-coder reliability assessments will be conducted on approximately 25% of transcripts during both structural and content coding. Discrepancies in coding will be resolved through analyst discussions; transcripts will be re-coded and the codebook revised accordingly. Once coding is complete, we will examine code frequencies across transcripts to identify salient factors for each interview group, followed by comparing and contrasting factors between groups. To conclude analyses, analytical memos and reports will be written, describing the factors influencing success in maintaining the functional benefits of obesity treatment over time, together with illustrative quotes.

Aim 2. Feasibility: Proportion of participants recruited will be calculated as the number of participants deemed potentially eligible and contacted for enrollment divided by the total number of participants enrolled. Proportion retention will be computed by dividing the number

of retained participants at the end of the intervention by the total number randomized into the study. Fidelity: Proportion adherent to the tele-nutrition diet and tele-exercise intervention. Acceptability: Levels of attrition will be calculated and satisfaction will be assessed with survey items on a Likert-scale and focus group.

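### The recruitment proportion is defined upside down (contacted over enrolled), so it can never fall below 100% and rises as recruitment worsens; retention in Section 6 is divided by a randomized count in a single-arm study

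*Combined protocol and SAP*

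**What the plan says.** Section 6, under Aim 2 Feasibility, opens the definition with "Proportion of participants recruited will be calculated as" and completes it as the "number of participants deemed potentially eligible and contacted for enrollment divided by the total number of participants enrolled". Table 4 in Section 5, in the row headed Feasibility, repeats it almost word for word: "number of patients deemed potentially eligible and contacted for enrollment divided by the total number of patients enrolled". No other place in the document gives the ratio the other way round.

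The next sentence of Section 6 defines retention by dividing the number "of retained participants at the end of the intervention by the total number randomized into the study". Table 4 defines the same measure differently, by "dividing the number of retained subjects at the end of the intervention by the total number of participants". The Study Summary describes Aim 2 as a "Single-arm pilot intervention investigating the feasibility, fidelity, and acceptability" of the tele-intervention, and Section 6 itself refers to one group when it describes the analysis of the feedback session.

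Feasibility, acceptability and fidelity of the intervention form a primary endpoint in Section 3.2. The Aim 2 objective in Section 2 spells out feasibility as recruitment and retention.

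**The concern.** A recruitment proportion should give the share of those approached who joined: it lies between 0 and 1, and a larger value means better recruitment. The formula in the plan does neither. The count that must be the larger is on top, so the result cannot be below 1, and a study that approached more people for each enrolment would report a higher figure.

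The pilot is meant to supply preliminary data for a larger trial, and recruitment yield is one of the inputs to planning that trial. An analyst who follows the text reports a primary feasibility measure that is impossible as a proportion. An analyst who silently inverts it departs from a prespecified definition that is stated identically in two places.

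The retention sentence has a smaller fault of the same kind: taken by itself, it names a denominator that does not exist in this design.

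**Working it through.** **Inputs**

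- E, number enrolled in Aim 2: approximately 15, planned to yield 10 completers with 30% dropout (Section 5, Aim 2). The Study Summary allows up to 20.
- C, number potentially eligible and contacted: not given anywhere. The values below are assumptions for illustration.
- Order of events: Section 4.1 says "Study staff will contact potential subjects to request their participation in the study", with telephone screening and consent following; Section 4.2 gives the same order. The enrolled are therefore a subset of those contacted, so C ≥ E.

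**The plan's own figure.** 10 / (1 − 0.30) = 14.29, rounded up to 15. The planned enrolment reproduces. The plan sets no numerical target for recruitment, so there is no other figure to reproduce.

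**Direction of the ratio.** As written, the measure is C/E. Since C ≥ E, C/E ≥ 1, with equality only when everyone contacted enrols. The recruitment proportion is E/C, which lies between 0 and 1. The two are reciprocals, so whenever one falls the other rises.

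**With E = 15.** The last column is the exact (Clopper-Pearson) 95% interval for E/C.

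| C (assumed) | As written, C/15 | Recruitment proportion, 15/C | 95% CI for 15/C |
|---|---|---|---|
| 15 | 100% | 100% | 78.2% to 100% |
| 20 | 133.3% | 75.0% | 50.9% to 91.3% |
| 30 | 200% | 50.0% | 31.3% to 68.7% |
| 45 | 300% | 33.3% | 20.0% to 49.0% |
| 60 | 400% | 25.0% | 14.7% to 37.9% |
| 100 | 666.7% | 15.0% | 8.6% to 23.5% |

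**Sensitivity to E.** With E = 10, C from 15 to 100 gives 150% to 1000% as written. With E = 20, C from 20 to 100 gives 100% to 500%. The conclusion does not depend on the enrolment figure.

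**Retention.** Section 6 divides by the number randomized. No allocation step is described anywhere, so taken literally that count is zero and the ratio is undefined. With the number enrolled as denominator and the planned 10 completers of 15, retention is 10/15 = 66.7% (exact 95% CI 38.4% to 88.2%), and attrition is 5/15 = 33.3%.

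**The case against.** The strongest reply is that little is lost in practice. The label makes the intention plain, the correct proportion is the reciprocal of the written one, and both come from the same two counts. No progression threshold, test or sample-size calculation uses the ratio, and enrolment continues until there are 10 completers whatever its value. On this view the worst outcome is a mislabelled descriptive figure. These statements are accurate, and they mean the error costs no data. They do not make the definition right: label and formula contradict each other, both defining passages carry the same error, and nothing else in the document corrects it.

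A second reply is that no planned confidence interval fails, because Section 6 plans intervals for retention, adherence and attrition and does not list recruitment. That stands. A binomial interval cannot be computed for a ratio above 1, but an interval for recruitment is an addition recommended here, not a repair of something already planned.

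A third is that the retention wording is a slip with an obvious reading, since Table 4 divides by all participants and uses the same base for attrition and both adherence measures. That also stands. By itself it would be an inconsistency to tidy, and the weight of this point rests on the recruitment ratio.

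**Conclusion.** The concern holds. The recruitment measure is inverted in both places that define it. It is never below 100% and moves in the wrong direction, and it is one of the two components of feasibility, a primary endpoint; in Table 4 it is the only item under the Feasibility heading. With 15 enrolled and 20 to 60 contacted, the reported figure would be 133% to 400%, where the recruitment proportion is 75% to 25%. Those sizes depend on the assumed numbers contacted. The inversion depends only on enrolled participants being drawn from those contacted, which Sections 4.1 and 4.2 establish.

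The reference to randomization in the retention definition is a genuine error for a single-arm study and conflicts with Table 4, which shows the evident intent. The definitions must be corrected before feasibility is reported.

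**What to change.** - In Section 6 (Aim 2, Feasibility) and in the Feasibility row of Table 4, define the recruitment proportion as the number enrolled divided by the number potentially eligible and contacted.
- Add a 95% confidence interval for it, exact (Clopper-Pearson) or Wilson, alongside those already planned for retention, adherence and attrition.
- In the retention sentence of Section 6, replace the number randomized with the total number enrolled (consented) in Aim 2. State in Section 6 and Table 4 that retention, attrition and adherence all use this denominator.

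The cost is a few words in two places. No new data, change of conduct or participant burden is involved, provided the number contacted is logged during recruitment, which the measure requires in either direction.

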8. What were your expectations of losing weight?
 - a) What were you hoping to change, achieve?
 - b) Were those expectations met? Not met?
9. Has COVID-19 impacted your nutrition and/or physical activity? If so, how? If not, why?

Environment

1. How does your family/friends influence your eating/exercise habits?
2. What do you feel are your main barriers to healthy eating/exercise?
3. How does your culture/community affect your eating/exercise habits?
4. While you were participating in the _____ study, where did your support come from?
5. When you were in the study how did your social support network (friends, family, colleagues) react?

AIM 1b: Develop novel, customizable tele-programs of nutrition and exercise to maintain and extend legacy benefits of a recent obesity intervention: Creation of tele-intervention protocols for testing

The information gained from the individual interventions, combined with our expertise in nutrition and exercise interventions in obese, frail older adults and our established experts in tele-health and behavior science will inform the content of Tele-nutrition and Tele-exercise Legacy Intervention. Furthermore, protocol development for the Legacy Intervention will employ Social Cognitive Theory³ components that are key to maintaining behavior change. Expected Findings: we anticipate the “Legacy Intervention” will include cognitive behavioral strategies (e.g., goal setting, self-monitoring, and social support) and draw upon a toolbox of e-approaches, including daily and weekly text reminders, virtual exercise classes, virtual individual and group nutrition classes, and step tracking device.

AIM 2: Determine the feasibility, acceptability, and fidelity of a 3-month lifestyle enhancing tele-intervention: Pilot intervention trial

The 3-month tele-nutrition and tele-physical activity intervention developed in Aim 1b will be pilot-tested in older adults who, within the last 3 months, successfully completed a lifestyle intervention and meet the inclusion criteria in Table 3.

Successful completion of a lifestyle intervention: lost at least 3% body weight and increased SPPB score by 1 point or increased their 6MWT by 50 meters from their baseline.

We will enroll participants until we reach a total of 10 study completers. We anticipate enrolling approximately 15, allowing for a 30% dropout rate.

Table 3. Inclusion/Exclusion Criteria Aim 2

Inclusion Criteria	Exclusion Criteria

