time. Their decision not to participate or to withdraw from the study will not involve any penalty or loss of benefits to which they are entitled, and will not affect their access to health care at Duke. If they withdraw from the study, no new data will be collected for study purposes other than data needed to keep track of their withdrawal. If they withdraw from the study all data and samples that have already been collected for study purposes will be used unless a written request for all data to be destroyed is received. Participants who withdraw from the study will discontinue all study procedures.

Benefits

A number of potential health benefits that may accrue to participants and important scientific knowledge will likely result from this work. We expect that participants will achieve lifestyle modifications that could be sustained as a part of their personal health regimen in the setting of their community environment. Additionally, information collected from this study will benefit others through a greater understanding of how to best maintain physical function following an intensive weight loss intervention.

6 Statistical Plan

This is a pilot study that will be used to generate preliminary data for a larger clinical trial. The data analysis for both Aims are outlined below:

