We will calculate these rates of retention, adherence, and attrition and their respective confidence intervals overall. While non-powerful, in a series of sensitivity tests, we will assess if adherence overall was impacted by demographic/socioeconomic variables.

We will employ a simplified applied thematic analysis for the feedback session recording and transcript following a similar approach to 1a above, less the NVivo interface and group comparison given the single group. Assessment of our measures used with screening/recruitment, adherence/retention, attrition/participant satisfaction, physical function, and self-efficacy will inform our feedback session interview guide where we will examine aspects of the program in-depth from participants' perspectives. This will allow us to examine individual level success through our objective intervention documentation in tandem with rich data from participants during the feedback session.

For physical function outcome measures a repeated measures analysis of variance will be employed to determine differences between timepoints, followed by pairwise comparison of each time point to the baseline time point.

7 Safety and Adverse Events

Oversight and Reporting: [name] will be responsible for the operation of this research study according to the study's protocol and IRB policies. Any serious adverse event, study-related or not study related will be reported via email to the Duke University IRB within 24 hours of learning about the event. Within 5 business days following the initial report, a Notification of a Problem or Event Requiring Prompt Reporting Form will be sent to the Duke IRB. This study is not an intervention and thus will not have a safety monitoring board, however the investigator will submit the number of adverse events, complaints, withdrawals, and protocol violations to the Duke University IRB. In addition, the PIs will review quarterly adverse event reports and make adjustments to the protocol if needed.

We expect adverse events to be limited to loss of protected health information. The study team has outlined procedures for data management to protect against loss of data (detailed below). Breaches in data security will be reported within 24 hours of detection, and a plan for management of the breach and modification of data security procedures will be developed within 3 business days, if applicable.

8 Data Handling and Record Keeping

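### Change in SPPB and 6MWT is to be tested by repeated-measures ANOVA, with no rule for incomplete series and no confidence interval, although about 5 of 15 are expected to drop out

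*Combined protocol and SAP*

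**What the plan says.** Section 6 (Statistical Plan, Aim 2) deals with physical function in one sentence. The main analysis is stated thus: "a repeated measures analysis of variance will be employed to determine differences between timepoints". The second half of that sentence sets the contrasts, which come next: "followed by pairwise comparison of each time point to the baseline time point". Table 4 in Section 5 lists SPPB and 6MWT as function measures at 0, 6 and 12 weeks.

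Section 6 plans intervals for the rates: "We will calculate these rates of retention, adherence, and attrition and their respective confidence intervals overall". It plans none for change in function. No section gives an analysis set, a missing-data assumption or a sensitivity analysis for missing SPPB or 6MWT values. The sensitivity tests that Section 6 mentions concern adherence by demographic and socioeconomic variables.

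On numbers, Section 5 (Aim 2) says: "We will enroll participants until we reach a total of 10 study completers". It adds: "We anticipate enrolling approximately 15, allowing for a 30% dropout rate".

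On withdrawal, the text under Alternatives to Participation says that "no new data will be collected for study purposes other than data needed to keep track of their withdrawal", and that "all data and samples that have already been collected for study purposes will be used" unless the participant asks in writing for the data to be destroyed.

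On purpose, Section 6 opens: "This is a pilot study that will be used to generate preliminary data for a larger clinical trial". Section 3.2 names feasibility, acceptability and fidelity as the Aim 2 primary endpoints. Section 2 adds function after them.

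**The concern.** Incomplete series are built into the design: the plan expects leavers and stops measuring them when they withdraw. The classical repeated-measures ANOVA needs a value at every visit. Its omnibus test would drop each leaver's baseline value, any week-6 value they gave, and also any completer who missed week 6. A week-6 against baseline comparison run as a paired test could still keep people who left later, but the 12-week change would rest on those who stayed.

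The programme aims to maintain function, and people who are losing it may be the ones who leave. Enrolling until 10 complete fixes the number of completers but does not remove that selection. A larger trial needs an estimate of change and its precision. A test result without an interval does not show that precision, and an estimate from completers may be too favourable.

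**Working it through.** **1. The plan's own enrolment figure.** 10 completers / (1 − 0.30) = 14.3, rounded up to 15. This agrees with Section 5. Expected leavers: 15 − 10 = 5 (33%), or 15 × 0.30 = 4.5.

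**2. Values that a classical omnibus test would not use** (15 enrolled, 5 leave, no other gaps), per outcome:
- All leave before week 6: collected 15 + 10 + 10 = 35, unused 5, and 5/35 = 14%.
- All leave after week 6: collected 15 + 15 + 10 = 40, unused 10, and 10/40 = 25%.

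**3. Precision with 10 completers.** The 95% half-width for a mean change is t(0.975, 9) × SD/√10 = 0.715 × SD. The documents give no SD of change, so these are assumed ranges:

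| Outcome | Assumed SD of change | Half-width, n = 10 |
|---|---|---|
| SPPB (points) | 1.0 / 1.5 / 2.0 | 0.72 / 1.07 / 1.43 |
| 6MWT (m) | 40 / 50 / 60 / 70 | 28.6 / 35.8 / 42.9 / 50.1 |

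The plan's eligibility rule counts 1 SPPB point or 50 m as an improvement. At an SPPB SD of 1.5 the half-width already exceeds 1 point.

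**4. Bias of a completers' mean.** Bias = share lost × (mean change in completers − mean change in leavers). With 5 of 15 lost, leavers worse by 0.5, 1 or 2 SPPB points give 0.17, 0.33 or 0.67 points. Leavers worse by 25, 50 or 100 m give 8.3, 16.7 or 33.3 m.

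**5. Simulation with equal correlation between visits.** 3,000 trials per case, 15 enrolled, one third leaving. Assumed: visit means 9.0/8.5/8.0 (true 12-week change −1.0), SD of change 1.5, correlation 0.719, logistic dropout with slope 1.0 per point of decline. The mixed model here has a random intercept, which is the correct covariance in this setting.

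| What drives dropout | Completers: mean (RMSE) | Mixed model: mean (RMSE) |
|---|---|---|
| Observed week-6 decline | −0.73 (0.54) | −1.00 (0.46) |
| Decline, leaving before week 6 | −0.72 (0.55) | −0.79 (0.52) |
| Unseen week-12 change | −0.46 (0.69) | −0.61 (0.57) |
| Nothing (random) | −1.00 (0.48) | −1.01 (0.45) |

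The first row agrees with step 4: a bias of 0.27 over one third lost implies a gap of 0.27 × 3 = 0.81 points. With the dropout slope halved, the completers' mean in that row is −0.83. The model was closer to the truth than the completers' mean in 55–77% of single trials.

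**6. Which covariance.** The simulation was repeated with adjacent visits correlating 0.85 and weeks 0 and 12 correlating 0.72. With dropout following week-6 decline, completers gave −0.70 (RMSE 0.56), the random intercept −0.86 (0.46), and unstructured REML −1.00 (0.50; about 700 trials). Coverage of nominal 95% intervals:

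| What drives dropout | Completers | Random intercept | Unstructured |
|---|---|---|---|
| Observed week-6 decline | 0.908 | 0.882 | 0.918 |
| Nothing (random) | 0.951 | 0.897 | 0.946 |
| Leaving before week 6 | 0.909 | 0.840 | not run |
| Unseen week-12 change | 0.800 | 0.785 | not run |

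A separate check (250 trials per case) with unstructured REML and conservative degrees of freedom gave mean changes of −1.05 and −0.99, with coverage 0.94–0.96. The random intercept covered 0.88–0.91 there.

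**The case against.** The strongest case against is that the plan is under-specified and not shown to be wrong. Section 6 does not name the form of ANOVA and does not say complete cases only. That stands: the loss of data is conditional on the classical form, which is the usual meaning of the words used.

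A reader might infer that the plan contradicts itself, because it says that collected data will be used. The documents do not support this. That sentence is a data-retention statement about withdrawal, not an analysis-set rule, and leavers' data can still enter the attrition and retention rates and a week-6 comparison.

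A reader might also take the Study Summary's ceiling of 20 for Aim 2 to mean that half of those enrolled could be left out (10 of 20). The ceiling is a cap. At the plan's own 30% dropout, the probability of needing 20 or more to reach 10 completers is only about 3%.

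It is also fair that the benefit depends on the dropout mechanism. With random dropout there is no bias to remove. If decliners leave before week 6, the random-intercept model recovers only 0.07 of a 0.28-point bias. With no control arm, neither analysis can attribute change to the programme.

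Finally, one added line asking for mean change with a 95% interval, the number per visit and a rule for incomplete series would close much of the gap without prescribing a model. That is a reasonable minimum, but an estimate from completers would still be biased when dropout follows decline already observed. An all-available-data model can correct that case.

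**Conclusion.** The concern holds in a limited form. Section 6 plans no interval for change in function and does not say how incomplete series enter the analysis, although about 5 of 15 are expected to leave. If the ANOVA is run in its classical form, it omits about a third of those enrolled and 14–25% of the values collected. If dropout also follows observed decline, the completers' 12-week SPPB change is about −0.7 against a true −1.0. The second figure rests on assumed means, SDs, correlations and dropout strength, none of which the documents give. The missing interval and the missing rule do not depend on the simulation.

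It would be wrong to infer that the pilot's main results are at risk. Function is supportive, and the choice of model for mean change does not alter the primary feasibility, acceptability and fidelity rates. Nor do the documents show that dropout will be informative. The change is worth making because the data are meant to inform a larger trial, but the gain in one trial of this size is modest.

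**What to change.** Replace the ANOVA sentence in Section 6 with:

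> SPPB and 6MWT will be analysed with a mixed model for repeated measures (REML, time as a category, unstructured covariance across the three visits, small-sample degrees of freedom such as Kenward-Roger) using all available values from all enrolled participants. Mean change from baseline at 6 and 12 weeks will be reported with 95% confidence intervals and the number contributing at each visit. The model assumes that dropout depends only on observed data; baseline and last observed values will be shown for leavers and stayers.

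A random intercept alone should not be fixed as the covariance. When adjacent visits correlate more than distant ones its intervals are too narrow (coverage about 79–90% in step 6), and it covered less well than the completers' analysis in all four cases.

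The cost is wording and one standard model, with no extra data or visits. The downsides are a slightly less simple analysis, six covariance parameters (three variances and three covariances) estimated from about 15 people, intervals that stay wide (about ±0.72 SD of change at n = 10), and remaining bias if dropout depends on decline that was never observed.
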